Since the standard of care is narcotic usage to manage the significant pain that complex spinal surgery causes, it is understandable that methadone could be a desirable therapy to promote sustained pain control and early ambulation in these patients. It is our hypothesis that methadone use intraoperatively will result in earlier time to ambulate post op and better ability to participate with post-operative PT evaluation, lower narcotic usage, earlier discharge, and improved scores on clinical outcome scales including the Oswestry Low Back Pain Disability Questionnaire and the Short Form 36 Health Survery. It is also foreseeable that since methadone would be administered while the patient was sedated intraoperatively, it could prevent the association between the analgesia and euphoria that may result from self- or nurse-administered narcotics, such as with a PCA, which could promote early tolerance or reliance. Randomization of patients between methadone administration and standard intra-operative narcotic administration allows for controlled and accurate investigation of subjects compared to the current standard of care.

• Clearly state target population and recruitment methods

We would screen the first 200 consecutive patients to determine whether inclusion criteria are met, with an end goal of 120 patients who will complete the study and 60 control subjects who receive the current standard of care in a 1:1 randomized fashion. Patient will be recruited in office at time of consent for surgery by the principal investigator.

• State inclusion/exclusion criteria clearly

Inclusion criteria:

Patients undergoing elective lumbar transforaminal interbody fusion or lumbar laminectomy and posterolateral fusion will be enrolled in the study and consented for intraoperative single-dose methadone administration or standard narcotic regimen administration in a 1:1 block randomization plan. Patient may undergo one or two spinal level fusions and in blocks of 5, will be assigned to intervention or control groups in a manner that will be blinded to both the clinical team and the patients.

o Exclusion criteria:

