The patients will be randomized with 1:1 ratio of intervention and control groups, in blinded blocks of 5, randomly assigned by software used on www.randomizer.org to create 60 study patients and 60 control patients. Envelopes will be used to assign the patients in blocks of 5. Therefore in the first group is to be a control group, the first 5 patients will be controls, then the next group of 5 will be randomly assigned to control or intervention group based on a randomized protocol listed on a study envelope. Overall the blocks of 5 will create even groups of control and intervention patients overall to reach the 120 patient goal. One member of the study team, not involved in the surgical procedure and post-operative pain evaluation will be designated unblended and will communicate with the anesthesiology team pre-operatively to determine whether the patient is to receive methadone or not. The anesthesia team will be responsible for allocation and administration of the methadone, in addition to the standard fentanyl and ketamine, from the Montefiore pharmacy which is already available for intra-operative use as an alternate narcotic regimen. Post-operatively, blinded team members will collect pain data, as well as time to ambulation and discharge data. The pain measures will be patient derived, and time to event data will be part of the patient's chart.

Describe what safety outcomes will be monitored

Safety outcomes to be measured as stated in the adverse events section of this protocol include risks of using any opioid narcotic, which include overdose leading to respiratory depression, dependence and QTc prolongation. Psychological risks include obtunded, lethargic state or altered mental status due to long half-life and opioid effects post-operatively and any resultant mental distress, especially in opioid-naïve patients

Include a data safety monitoring plan

A data safety monitoring plan is included in section 7, under the subheading "Describe methods for interim analyses or early stopping, if applicable"

➤ For Observational studies

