• Describe predictors of interest along with potential confounders and effect modifiers Predictors of interest include drug abuse history and/or behavior, as well as anticipated benefit from history of medication usage in the literature. Potential confounders include previous narcotic use history, narcotic tolerance/dependence in patients not otherwise excluded during recruitment, variable pain thresholds and tolerance amongst different patients, duration and complexity of surgeries, as well as variable renal clearance. Many of these are also effect modifiers.

• Describe matching criteria, if applicable

Matching criteria will not be used at this study will be structured as a randomized control trial.

• Describe duration of follow-up, and timing of data collection

Post-operative imaging will be reviewed to determine successful decompression and instrumentation. Data collection will be done during patient's hospital stay. Patients will be asked about their post-operative pain at 4 hour intervals, and data regarding their overall narcotic usage and their time to ambulation will be recorded from the medical record. Follow-up will then consist of: 1 week for phone call by spine NP, 2 week evaluation as is standard for all post-operative patients.

• Describe the planned interventions and their timing.

A study participant will be randomized ahead of time to be administered methadone or the current standard of care in blocks of 5 blinded to clinical personnel. If the patient is assigned to the methadone group, the anesthesiology team will be given this information and the anesthesiologist assigned to the Revised 4/17/13, 6/23/15

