A prospective patient will be called before a planned surgical procedure and the outline of the study will be presented to them. If they are interested in participating, a further discussion will be undertaken immediately before their surgery in person and they will be asked to sign a consent form at that time. They will be reminded of their ability to rescind consent at any time and of the randomization process. For those patients screened in the outpatient clinic, information regarding the study will be presented to them upon agreeing to undergo surgery, however since they will need to pass pre-operative testing before they will be cleared to undergo surgery, only on the morning before surgery will they be asked to officially sign the study consent form.

• Who will obtain consent?

Consent will be obtained but the key personnel listed in this study proposal.

• Where will consent be obtained?

Consent will be obtained in the office at the time of consent for surgery verbally, confirmed over the phone on the day before surgery, and formally signed in the ambulatory surgery area prior to surgery. This redundant process will further ensure that patients understand the purposes of the surgery and have enough time to make an informed decision regarding their participation.

 Provide clear justification if a waiver or alteration of the informed consent process is requested.

Not applicable.

- If minors are included, describe the plan for parental approval and child assent. Not applicable
 - Describe any costs or remuneration:
 - State any reimbursement or remuneration, including the pro-rating scale if multiple visits are required.

- Clearly identify tests and procedures as for Research Purposes or Standard Clinical Care.
- Include a listing of any costs (tests/procedures/supplies which are the responsibility of the subject).

There will be no costs or remuneration for the study, as the key personnel involved will not be financially compensated in any way and the intervention as well as all data collected is considered part of routine post-op surgical care. The patients will not be reimbursed for participation in any part of the study and they will be reminded that their care will otherwise not be altered as a result of participation. They will be responsible for all the costs of the surgical procedure, either directly, through insurance, or through Montefiore, as would any individual undergoing surgery.

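### Allocating one arm to each run of five consecutive patients randomises 24 runs, not 120 patients, and yields the planned 10:10 interim split in only 41% of sequences

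*Combined protocol and SAP*

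**What the plan says.** Section 2 (Study Design), under randomization and blinding procedures, states a 1:1 ratio, with patients "randomly assigned by software used on www.randomizer.org to create 60 study patients and 60 control patients". It continues: "Envelopes will be used to assign the patients in blocks of 5". The mechanism is then spelled out: "Therefore in the first group is to be a control group, the first 5 patients will be controls", and "then the next group of 5 will be randomly assigned to control or intervention group". Balance is claimed only across blocks: "Overall the blocks of 5 will create even groups of control and intervention patients overall to reach the 120 patient goal".

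Two other places in Section 2 repeat the block size without giving a different mechanism. The inclusion criteria put it this way: "in blocks of 5, will be assigned to intervention or control groups in a manner that will be blinded to both the clinical team"; they blind patients as well. The description of interventions and timing says: "A study participant will be randomized ahead of time to be administered methadone or the current standard of care in blocks of 5".

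Section 5 (Informed Consent) has consent given verbally in the office, confirmed by phone, and "formally signed in the ambulatory surgery area prior to surgery". No section says that the arm is disclosed only after that signature.

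Section 7 (Data Analysis) compares the arms with two-sample t-tests on individual patients. It schedules an interim comparison after 20 patients complete, expects about ten per arm, and bases its interim error calculation on ten per arm.

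**The concern.** In ordinary blocked randomisation each block contains both arms. Here each block contains one arm, so blocking works against its purpose: arm sizes move in steps of five, and five consecutive patients always share a treatment.

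Three things are at stake.

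- **Interim look.** The monitoring committee may face a lopsided comparison or none at all.
- **Concealment.** Within a run, every arm after the first is determined. One disclosure reveals the rest of that run, and the plan does not exclude disclosure before consent is signed.
- **Analysis.** Consecutive patients share a calendar period and perhaps staff. If their outcomes are correlated, a patient-level t-test overstates the precision of the comparison.

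The first two need no assumption about correlation. The third does.

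**Working it through.** **Inputs.** 120 patients, 60 per arm, runs of 5 (Section 2, randomization). Interim at 20 patients, about 10 per arm; effect size 0.56 SD, significance level 0.05, power 80%, 51 per group calculated and 60 planned (Section 7). No drop-out expected (Section 3).

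**The plan's own sample size.** n = 2(1.960 + 0.842)² / 0.56² = 50.1, rounded up to 51 per group (two-sided). This matches. With 60 per arm and independent patients, a t-test on 118 df has 86% power at 0.56 SD. The sample size is therefore sound for individually randomised patients.

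**Number of randomised units.** 120 / 5 = 24 runs. Sixty per arm implies 60 / 5 = 12 runs per arm.

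**Interim split, enrolment order.** The first 20 patients are 4 of the 24 runs; C(24,4) = 10,626.

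- 10:10: C(12,2)² = 66² = 4,356; 4,356 / 10,626 = 41.0%.
- 5:15 either way: 2 × 12 × 220 = 5,280; 5,280 / 10,626 = 49.7%.
- One arm empty: 2 × 495 = 990; 990 / 10,626 = 9.3%.

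No near miss is possible, because an arm can only have 0, 5, 10, 15 or 20 patients. Fixing the first run as control leaves the 10:10 figure unchanged: 11 × 66 / 1,771 = 41.0%. If each run were an independent coin toss, it would be 6/16 = 37.5%, but 60:60 at the end would then occur with probability only 16%.

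**Interim split, completion order.** The plan counts completers. Assume that each patient's place shifts by a normal amount with SD 1, 2 or 4 places. In simulation a split between 8:12 and 12:8 still occurs in about 41% each time, and an empty arm in roughly 7%, 6% and 4%.

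**Cost of a 5:15 split.** In SD units the standard error is √(1/5 + 1/15) = 0.516, against √(2/10) = 0.447 at 10:10, a ratio of 1.155. With a normal outcome and known SD, the one-sided null chance of reaching the plan's one-SD line is 1 − Φ(1/0.516) = 2.6% per measure, against 1 − Φ(1/0.447) = 1.3% at 10:10. The plan's own figure of about 1 in 100,000 is not reproduced even at 10:10. That is a separate error, and the allocation does not cause it.

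**Predictability.** In each run, four arms follow from the first: 24 × 4 = 96 of 120 (80%).

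**Analysis, conditional on within-run correlation ρ.** The documents give no value, so ρ is assumed. Type I error is for the planned t-test, by simulation. Power is for a run-level test on 22 df with noncentrality 0.56 / √(2(1 + 4ρ)/60).

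| ρ | Type I error, planned t-test | Run-level power at 0.56 SD |
|---|---|---|
| 0 | 5.0% | 83% |
| 0.01 | 5.5% | 82% |
| 0.05 | 7.3% | 76% |
| 0.10 | 9.9% | 70% |

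Run-level power drops below 80% at ρ of about 0.024. That threshold depends on the method: a simple design-effect approximation (60 / 1.2 = 50 effective patients per arm) reaches 80% only at ρ of about 0.05.

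**The case against.** The strongest reply is that the harm is potential. Ten per arm is the correct expected number, and the plan says only that it is approximate. The interim look is advisory. The separate safety rules in Section 7, on excess adverse events and on a death caused by methadone, do not need a balanced split. Only the empty-arm case defeats the comparison outright.

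On concealment, disclosure is limited to one unblinded team member and the anesthesia team, and the clinical team is blinded. Screening is of consecutive patients, and verbal agreement comes before signature. Randomising ahead of time may mean only that the list is prepared in advance. The 80% is a worst case, for someone who knows where every run starts and its first arm. On analysis, with zero within-run correlation the t-test holds its level, and no correlation is documented. Recruitment is through one investigator's office, so clustering by site is not a source, although drift over time or changes of staff could be.

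Much of this stands. No leak is shown, the 80% is an upper bound, and the type I error and power effects are conditional. None of it changes the mechanism: no section offers an alternative to the worked example, and an odd block cannot be balanced 1:1. An expected value of ten does not help when the nearest other split in enrolment order is 5:15. The safety rules do not restore the scheduled comparison.

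**Conclusion.** The concern holds, and the allocation text must be changed. As written, 24 runs of five are randomised. The interim comparison has its planned 10:10 split in 41.0% of sequences, 5:15 in 49.7%, and an empty arm in 9.3%. These figures assume 12 runs per arm, which follows from the 60 and 60 target, and enrolment order. Under the assumed shifts in completion order, a split near 10:10 is no more likely. Up to 96 of 120 arms follow from the first arm of their run, although the documents do not show that recruiters or assessors learn any arm. The inflated type I error and lost power arise only if outcomes within runs are correlated, and their size is unknown.

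**What to change.** **Allocation.** Replace every statement about blocks of 5 in Section 2 (inclusion criteria, randomization and blinding, interventions and timing). Delete the worked example and the sentence claiming that such blocks give even groups. State instead that individual patients are randomised 1:1 in permuted blocks of randomly varying even size. For example, 12 blocks of 4 and 12 blocks of 6 in random order give 12 × 4 + 12 × 6 = 120 allocations, exactly 60 and 60. Withhold the block sizes from recruiting and clinical staff.

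**Concealment.** Use one sealed, opaque, numbered envelope per patient, opened by the existing unblinded team member only after the consent form is signed. State that order in Sections 2 and 5.

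**Runs already treated.** If any exist, keep them and account for the run in the Section 7 analysis, by a random effect or a run-level test with a small-sample correction.

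**What it gains.** At 20 patients in enrolment order the split is 10:10 in 78% of lists and 9:11 in 22%, with nothing worse. Under the same assumed completion shifts (SD 1, 2 and 4 places), 10:10 falls to about 71%, 62% and 49%, but a split between 8:12 and 12:8 still occurs in at least 99.9%. Someone who knew every block size and every past arm could be certain of 12 × 1.333 + 12 × 1.5 = 34 of 120 arms (28%), against 96 now. The multipliers are the mean lengths of the final same-arm stretch in blocks of 4 and 6.

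**What it costs.** A new list from the existing software, 120 envelopes and a protocol amendment. The unblinded member must be available between signature and surgery for each case, and there is slightly more analysis work if some runs have been treated. No extra patients are needed.

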Age <21 or >80, renal failure requiring dialysis or serum creatinine greater than 2.0, significant hepatic dysfunction (liver function tests greater than twice the upper limit), hepatic cirrhosis, pulmonary disease requiring home oxygen therapy, obstructive sleep apnea, severe heart disease, allergy to methadone, morphine, ketamine or fentanyl, **recent or distant history of opioid abuse,** opioid use equal to or greater that the equivalent of 10mg morphine per day, poorly managed psychiatric illness, a known history of alcohol abuse, morbid **obesity (for the purposes of this study body mass index > 50 kg/m2),** treatment with other NMDA receptor antagonists, HIV-1 protease inhibitors, erythromycin or ketoconazole, prolonged QTc on pre-operative EKG, and the refusal or inability to sign the consent form to agree to participate in this study.

State primary and secondary outcome(s)

The primary outcomes for the study include total narcotic dose post-operative, frequency of narcotic use, the time to first ambulation after surgery with PT, length of stay, disposition (i.e. level of rehabilitative care), and improvement on clinical questionnaires in the intervention group as compared to the control group. Secondary outcomes include better subjective pain control, need for post-operative course of

dexamethasone for post-operative/post-fusion radiculopathy or neurapraxia/neuropathy and fusion at 3-6 months.

> For Randomized clinical trials

• Indicate whether a parallel or crossover study, and the number of treatment groups
The study will take the form of a parallel, 2 arm analysis of a methadone treatment group or a
group receiving the current standard of care without intra-operative methadone administration.

• Describe randomization and blinding procedures

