The sample size was determined using the Gottschalk study listed in the reference section which used methadone vs. sufentanil in 29 patients undergoing lumbar fusion surgery and the measures for pain level and total narcotic usage at 48 hours to determine an 'n' for the total study population, using a power of 0.80. The details of the calculations is listed in the data analysis section (7a) below and calculated with the suggestion of the statistician on the IRB. The assumptions with which the outcomes are hypothesized are the result of previously published data using similar populations. Two sample t-tests are appropriate to determine statistical significance between mean pain scores between different patients in the control and study groups for each individual time point as there will be no censoring of the study data. Ranked T-test may also be used if outliers are present, however patients with unusual post-operative courses may be excluded if their reason for prolonged hospitalization is unrelated to immediate post-operative pain

control. The large sample size plans to take into account possible outliers that may not be included in final analysis, despite their mention in study write-up to determine why their post-operative hospitalization was prolonged. Additionally, data about patients' mean time to ambulation, mean time to discharge, and mean overall narcotic usage will be measured between the control and study populations. Data analysis will be performed with the assistance of the biostatistician listed as a member of the study team, [name], from the Albert Einstein College of Medicine, Division of Biostatistics. Thus, a sample of 60 completed methadone patients will be evaluated against 60 randomized, standard narcotic regimen controls. The mean data for control patients' pain ratings, narcotic usage, time to ambulation, and time to discharge will be obtained, the statistical deviation of this data will be measured and compared to subject data in all facets.

• Take into account anticipated drop-out or loss-to-follow up rate.

We intend to screen 200 patients to have 60 in each arm ultimately included in the study. Since the intervention is a single intra-operative occurrence, that when completed patients cannot reverse, we do not anticipate any drop-out. A two week follow-up visit is a required standard of care for all post-operative patients, without patient loss to follow-up historically. The study is completed at this point.

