The sources of recruitment will be patients presenting to the principal investigator's office for surgical evaluation and the methods as described above. Only patients who are already deemed surgical candidates beyond the scope of this study will be considered for inclusion into this study.

• Describe the method(s) for ensuring voluntariness of participation.

Patients will be free to refuse to enroll in the study and will be ensured that in no way will their care be altered due to their enrollment or refusal to participate in this study. All subjects will sign an informed consent form prior to enrollment in the study and reminded that they can reverse their consent and participation at any time.

• Describe the plan for Patient Privacy protection.

Patient health data and records will be handled with compliance of HIPAA regulations and will only be accessed on Montefiore computers by members of the study as outlined by the IRB form. All information will be taken from chart to a separate database and will be used in de-identified form only. **De-identifed data will be used for database purposes but a password protected master list matching subject number to MRN and name will be kept by the principal investigator, allowing identification of patients, if required.** We will use secure databases on encrypted Montefiore drives as our repository. They are safe, protected, and HIPAA compliant. All correspondence regarding this study will be through Montefiore secure email servers.

5) Informed Consent

• Provide an Informed Consent Form containing all of the necessary elements (see below).

An informed consent document is attached to this application, will use non-medical terminology, and will outline all aspects of this study to the patients, including a clear descriptions of all risks and benefits. Control and methadone intervention patients will be consented in the same manner and patients will be informed that they may not be administered methadone intra-operatively as part of the randomization process.

• Describe the informed consent process.

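### Nothing makes signed consent and confirmed eligibility a condition for assigning or releasing the arm, and groups of five fix the arm of up to 96 of 120 patients before they sign

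*Combined protocol and SAP*

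**What the plan says.** **Assignment.** Section 2, under planned interventions and their timing, states "A study participant will be randomized ahead of time to be administered methadone or the current standard of care". It does not say ahead of what. Under randomization and blinding procedures, one unblinded member of the study team "will communicate with the anesthesiology team pre-operatively to determine whether the patient is to receive methadone or not". The same paragraph describes allocation by whole groups, using envelopes: if the first group is a control group, "the first 5 patients will be controls, then the next group of 5 will be randomly assigned to control or intervention group".

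**Eligibility and consent.** The exclusion criteria in Section 2 include "the refusal or inability to sign the consent form to agree to participate in this study", alongside prolonged QTc, creatinine and liver-test limits. Section 5 describes verbal agreement in the office, confirmation by phone the day before, and a form that is "formally signed in the ambulatory surgery area prior to surgery". It explains that patients must first pass pre-operative testing, so "only on the morning before surgery will they be asked to officially sign the study consent form". Section 4 (voluntariness) adds: "All subjects will sign an informed consent form prior to enrollment in the study".

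**Counting.** Section 3 screens 200 patients to end with 60 per arm, describes the methadone group as completed patients, and says "we do not anticipate any drop-out", because the intervention is a single intra-operative event that cannot be reversed.

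**The concern.** Selection bias is kept out at entry by settling consent and eligibility before anyone who can influence them knows the arm. This plan does not state that order. One member of the team knows the allocation and anaesthesia is told it before surgery. The last eligibility criterion, a signature, is met only on the surgical unit.

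If the arm is known first, a patient could be accepted, turned away or withdrawn by someone who knows it. The groups compared would then no longer be the groups that were randomised. The loss would also be hard to see. The number randomised is never stated, no analysis set of all randomised patients is defined, and the write-up explanations promised elsewhere cover outliers, prolonged stays and deaths, not patients who were assigned an arm but did not sign or were not dosed.

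**Working it through.** **Step 1: the order of events, side by side.**

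| Event | When, according to the plan | Tied to signature or an eligibility check? |
|---|---|---|
| Arm assigned | Ahead of an unstated point (Section 2, planned interventions) | No |
| Arm released to anaesthesia | Before surgery (Section 2, randomization) | No |
| Pre-operative testing | Before clearance for surgery (Section 5) | Precedes signature |
| Form signed | Just before surgery, in the ambulatory surgery area (Section 5) | It is itself a criterion |
| Enrolment | After signature (Section 4) | Yes, but enrolment is never defined as opening the envelope |

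The text allows assignment after signature, and it equally allows assignment before it.

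**Step 2: the effect of groups of five.** Inputs: 120 patients and 5 per group (Section 2, randomization).
- Groups: 120 / 5 = 24.
- Patients who follow the first in their group: 24 × 4 = 96.
- Share: 96 / 120 = 80%.

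Once a group's envelope has been read for its first patient, the next four have an arm that is already fixed, and known to whoever read it, before they sign. Opening the envelope later in the day protects only the first patient of each group, 24 of 120.

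**Step 3: is power the problem?** Inputs from the power analysis in Section 7: difference d = 0.56 SD, alpha 0.05, 80% power. Sidedness is not stated; two-sided reproduces the plan's figure.
- n = 2(1.960 + 0.842)² / 0.56² = 50.1, rounded up to 51 per group, as stated. One-sided would give 40.
- Power = Φ(d√(n/2) − 1.96). At n = 60: Φ(3.067 − 1.96) = 86.6%.

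The plan gives no rate of loss between assignment and treatment, so the losses below are assumed.

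| Assumed loss | Left per arm, of 60 | Power at 0.56 SD | Allocated per arm to keep 60: 60/(1 − loss), rounded up |
|---|---|---|---|
| 5% | 57 | 84.8% | 64 |
| 10% | 54 | 82.9% | 67 |
| 15% | 51 | 80.7% | 71 |
| 20% | 48 | 78.3% | 75 |

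The margin from 51 to 60 absorbs a loss of about 15%.

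**Step 4: what arm-dependent loss would do.** This is an illustration; neither input is in the documents. Suppose a share q of one arm only is lost, and those patients' outcomes would have been g SD worse than the rest of that arm. The comparison shifts by q × g SD. With 60 analysed per arm, the standard error is √(2/60) = 0.183 SD. The two-sided error with no true effect is 1 − Φ(1.96 − qg/0.183) + Φ(−1.96 − qg/0.183). Days use the 6.7-day SD of time to discharge given in Section 7.

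| q | g | Shift (SD) | Shift (days) | Error at nominal 5% |
|---|---|---|---|---|
| 5% | 0.5 | 0.025 | 0.17 | 5.2% |
| 10% | 0.5 | 0.05 | 0.34 | 5.9% |
| 10% | 1.0 | 0.10 | 0.67 | 8.5% |
| 20% | 1.0 | 0.20 | 1.34 | 19.5% |

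Small or weakly selective losses do little. Larger, strongly selective losses matter, and a larger sample would not remove the shift.

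**The case against.** The best defence is that the plan already implies the right order. Section 4 has every subject sign before enrolment, Section 2 speaks of randomising a study participant, and the timing phrase may mean before incision, or only that the list and envelopes are prepared in advance, which is ordinary practice. Signature follows pre-operative testing, so EKG and laboratory failures should normally be known by then; they would fall after assignment only if the arm had been assigned days earlier, which the plan does not say. Morning refusals should be limited by the office and phone steps. Patients and the clinical team are to be blinded, and a refusal made without knowledge of the arm costs sample size but does not select by arm. The unblinded member is kept out of surgery and pain evaluation, and no section says that this person takes consent.

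Most of this stands, and it narrows the point. A reader might infer that patients are in fact randomised before consent, that refusals will depend on the arm, or that such losses are to be booked as screen failures. The documents say none of these. Nor do they support any count of selectively included patients.

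Two things survive. First, no sentence links the envelope to the signature, and Section 4 does not supply the link, because enrolment is not defined as assignment. Second, the unblinded member is not barred from consent or eligibility decisions (Section 5 leaves consent to the key personnel), and anaesthesia is told the arm. The groups of five then carry that knowledge forward to later patients even if every first envelope is opened at the right moment.

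**Conclusion.** The concern holds as a gap in the stated procedure: assignment and release of the arm are not conditional on signed consent and confirmed eligibility. On the plain reading of the group scheme, up to 96 of 120 patients have an arm fixed before they sign. That count rests on one envelope serving a whole group and being read for the group's first patient.

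Whether anyone would act on that knowledge cannot be told from the documents, and they give no rate of loss at this step. Power is a secondary matter and the stated 51 per group is unaffected. The exposure is to selection bias, whose size depends wholly on assumed inputs: negligible at the low end of the illustration, and about 1.3 days with a 19.5% error rate at the high end. It would be too strong to say that such bias could never be detected. A log of every allocation would reveal the losses, but the plan does not ask for one. The change is worth making before enrolment because it is cheap and because unrecorded losses cannot be recovered later.

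**What to change.** In Section 2, under randomization and blinding procedures and under planned interventions, replace the advance-randomisation wording with the following.

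1. There is one sealed, sequentially numbered envelope per patient, drawn from an individually randomised 1:1 list. This replaces assignment of whole groups of five.
2. The envelope is opened, and the arm released to anaesthesia, only after the consent form is signed and a dated checklist of all Section 2 eligibility criteria is complete.
3. The unblinded member takes no part in consent or eligibility decisions.
4. From opening, the patient counts as randomised. The patient is reported, and analysed in the assigned arm where outcome data exist, whether or not surgery or dosing follows.

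Section 3 should then state the number to be randomised as well as the number to be completed.

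The cost is protocol wording, a one-page checklist, a new list and a set of individual envelopes. If 60 treated patients per arm are still wanted, a few more allocations may be needed, as tabulated above. The practical downside is that anaesthesia learns the arm on the morning of surgery. The plan notes that methadone is already available from the pharmacy for intra-operative use, so this should be workable. No dose or clinical rule changes.
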